#### a. Position of the Investigator:

 Faculty or Non-Academic Equivalent Student Staff Resident/Fellow Other

### 4. What type of application is being submitted?

New Study Application (or Amendment/Continuing Review)

### 5. Title Of Study:

Thin film spectacle coatings to reduce light sensitivity and headaches in child and adolescent patients with migraine

### 6. Study Purposes and Objectives:

**Objectives:** The long-term goal of the project is to reduce the severity and frequency of migraines in child and adolescent patients who are sensitive to light. The goal of this protocol is to test an optical filter that blocks the wavelengths of light known to trigger migraines.

A co-PI is developing thin film coatings that will be applied to spectacle lenses. In this protocol, the investigators will determine the efficacy these prototype filters in a cohort of migraine patients.

7. **Is this a multi-site study, where more than one site needs IRB approval?**

Yes  No

8. **Background and Introduction:**

**Background and Introduction:** Nearly all migraine sufferers report sensitivity to light during a headache and a significant proportion of sufferers report light sensitivity between attacks. Light is also a common trigger for migraine headaches. Preliminary evidence indicates that migraine patients may be more sensitive to a particular portion of the visible spectrum. We hypothesize that if we could selectively block this portion of the visible spectrum, we could reduce the frequency and severity of headaches in migraine patients. The objective of this proposal is to develop coatings that can be applied to spectacle lenses, contact lenses, and light sources that will block the target wavelengths. The filters will then be tested in a cohort of adult patients with migraines. If successful, these filters could be a novel, non-invasive adjuvant in the treatment of migraines.

Approximately 9% of men and 18% of women are afflicted with migraines. (Stovner, 2006) Over 90% of patients with migraines report a sensitivity to light (photophobia) during headaches. (Evans, 2008) Some migraine sufferers report that light can trigger a migraine and some have a chronic sensitivity to light. (Main, 1997) Migraineurs are especially sensitive to non-incandescent lighting sources such as fluorescent lights, computer monitors, and gas-vapor lamps.

- **This research team will develop a light filtering technology to overcome the drawbacks of the FL-41 tint.** This filter coating is colorless, does not distort color perception, and can be used indoors or outdoors. The filter coating can be applied to not only plastic spectacle lenses, but also glass lenses, contact lenses, and even light bulbs and computer monitors. Furthermore, because the filter will block only the specific, target wavelengths it will likely be more effective than FL-41.

The filter coating will be different than FL-41 because it is not a *color filter*. Color filters are glasses or plastics that are doped with materials that naturally absorb portions of the light spectrum and have the drawbacks listed above. In contrast, the filter coating developed by this research team will use "thin-film" technology. Multi-layer "thin film" technology consists of alternating layers of transparent materials. The anti-reflection coating commonly found in optical shops is in fact a thin film applied to spectacles. Multiple layers of thin films can be designed to block narrow regions of the light spectrum.

IRB\_00065178

Created: 5/5/2013 4:38 PM

PI: [name]

Submitted: 7/17/2013

**Title:** Thin film spectacle coatings to reduce light sensitivity and headaches in child and adolescent patients with migraine

### 3. Participants

#### 1. Ages of Participants:

7 to 17 years old (Parental permission and assent form needed)

#### 2. Specific age range of participants (e.g., 7-12 years old, 60+, etc.):

8-18 years

#### 3. Indicate any vulnerable participant groups (other than children) included:

None

**If "Other", please specify:**

**If "None" and no children are involved, answer the following question.**

**Has the participant selection process overprotected potential subjects who are considered vulnerable so that they are denied opportunities to participate in research?**

Yes  No

#### 4. Number of participants to be included and/or enrolled in this entire study, across all study locations: 50

At Utah prior to October 2019: 50

#### 5. Characteristics of Participants/Inclusion Criteria:

1. Must be diagnosed with migraine with aura or migraine without aura
2. Must have at least 10 headache days per month

#### 6. Participant Exclusion Criteria:

1. Currently wearing a spectacle tint specifically prescribed for migraine or light sensitivity
2. Pregnant
3. Unwilling or unable in the judgment of the investigator to complete the study
4. Unavailable for any of the study visits
5. Light sensitive conditions: meningitis, iritis, blepharospasm, albinism
6. Degenerative diseases of the retina or optic nerve: diabetic retinopathy, ischemic optic neuropathy
7. Medications known to affect retinal or optic nerve function: hydroxychloroquine, chloroquine, ethambutol, amiodarone, erectile dysfunction drugs
8. Best corrected visual acuity less than 20/40 in either eye

#### 7. Is a substantial percentage of the participant population anticipated to be non-English speaking?

Yes  No

IRB\_00065178

Created: 5/5/2013 4:38 PM

PI: [name]

Submitted: 7/17/2013

**Title:** Thin film spectacle coatings to reduce light sensitivity and headaches in child and adolescent patients with migraine

## Vulnerable Populations

### Justification Requirements for the Inclusion of Vulnerable Populations

**1. How does the nature of the research require or justify using the proposed subject population?**

Very few migraine medications are specifically approved for use in the pediatric population. Specially coated spectacles could represent an effective, non-pharmacologic adjuvant in the treatment of migraine and light sensitivity in this population.

**2. Would it be possible to conduct the study with other, less vulnerable subjects?**

Yes  No

**If yes, justify the inclusion of vulnerable subjects:**

**3. Is this population being included primarily for the convenience of the researcher?**

Yes  No

**If yes, explain:**

**4. Does the scientific merit of the study warrant the inclusion of subjects who may either be susceptible to pressure or who are already burdened?**

Yes  No

IRB\_00065178

Created: 5/5/2013 4:38 PM

PI: [name]

Submitted: 7/17/2013

**Title:** Thin film spectacle coatings to reduce light sensitivity and headaches in child and adolescent patients with migraine

## 4. Study Information

1. **Design of Study (select all that apply):**

Survey/Questionnaire Research

Prospective Clinical Research

**If Other, describe:**

2. **Does your study involve the use of any placebo?**

Yes  No

3. **Length of entire study, from initiation through closeout:**

2 years

4. **How will participants be recruited or identified for inclusion in the study?**

a. **Select all methods that will be used:**

In-person contact (e.g., patients, students, etc.)

Written advertising (flyers, brochures, website postings, newspaper ads, etc.)

b. **Describe the recruitment/participant identification process in detail (e.g. who will review charts or records, who can refer participants to the study, where will flyers be posted, how often will recruitment letters be sent, when will follow-up phone calls be made, etc.):**

Subjects will be recruited directly from the clinics of the investigators. Flyers will be posted in the clinics. When potentially qualifying patients are identified, the clinic staff will contact the study coordinator to consent the patient that day, or if the patient/parent have given permission for the study team to contact them by phone, the clinic staff will provide patient/parent contact information to the study coordinator so she may follow up with the family about the study.

The study will be described to the patient and their family. Patients who express an interest will be invited to participate.

Patients/families may consent the same day they are informed about the study, or at a later time. They are welcome to arrange a separate appointment to consent and enroll in the study if they wish.

No database pools or participant pools will be utilized.

5. **How will consent be obtained?**

Informed Consent Process (with or without a document)

6. **Describe all the procedures chronologically, from screening/enrollment through study closeout, which will be completed in the research project.**

Once a subject meets eligibility criteria, informed assent will be obtained from the subject and informed consent will be obtained from the parent or guardian. With the help of their parent/guardian, subject will complete a brief questionnaire and the HIT-6 ("Headache Impact Test")

Subjects will be asked to try on two different test lenses - each has a mirror coating that reflects light. One blocks light at 480 nm (a bluish color) and one that blocks light at 620 nm (an orange color). Subjects will be asked which lens they think would help most with their headaches.

Subjects will be asked to complete a headache diary every day for one month. During this month, no study lenses are worn. At the end of the first month, subjects return for visit 2/4. They fill out another questionnaire, another HIT-6 and receive study glasses. Subjects who already wear glasses will receive study glasses customized to their prescription. Subjects who do not wear glasses will receive plain spectacles (no prescription) with the study coating. Subject will be asked to wear the study glasses during all waking hours. They will continue to fill out daily diary entries.

At the end of the second month, subjects return for visit 3/4. Study glasses are returned, the third set of questionnaires are completed. If the subject did not find the initial glasses to be effective, they will be asked if they'd like to try the other coating. If yes, they undergo a 4-week washout period and are given a second set of study lenses. If no, they continue in the study for four more weeks, as outlined below and exit the study.

For the third and final month, subjects are not wearing any study glasses. Diaries continue to be kept. At the end of the third month, subjects return for visit 4/4. Diaries are returned and a final set of questionnaires are completed.

Only non-conflicted members of the research team or third parties will collect and analyze all data for this research. All data will be masked during the collection and analysis phases of the research.

7. **Are all procedures for research purposes only (non-standard or non-standard of care procedures)?**

Yes  No

**If no, list the procedures that are performed for research purposes only (non-standard or non-standard of care procedures):**

8. **Is there a safety monitoring plan for this study?**

Yes  No

9. **Provide a summary of the statistical methods, data analysis, or data interpretation planned for this study. Factors for determining the proposed sample size (e.g., power) should be stated.**

Primary endpoint is a 30% reduction in HIT-6 scores. Secondary endpoints are a 30% reduction in headache frequency and severity. Questionnaires, HIT-6, and diary data will be used to evaluate these endpoints. The first and third months of the study serve as baseline data for subjects. Data collected during these two months will be compared to data collected during the second month, when study lenses are worn. A Student's T-test should be sufficient for evaluating these data.

IRB\_00065178

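### Item 9 calls a Student's t-test sufficient for two lens-free months against one lens month in the same children, but fixes neither the pairing, the unit of analysis nor how months 1 and 3 are combined

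*Protocol*

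**What the plan says.** Protocol section 4 (Study Information), item 6, describes a single cohort followed for a month without study lenses, a month with them and a month without. HIT-6 is completed at enrolment and at the visits closing months 1, 2 and 3. The diary is daily: "Subjects will be asked to complete a headache diary every day for one month". When the lenses are handed out, "They will continue to fill out daily diary entries", and the diary runs on through month 3. Children who did not find the first lens effective may have a washout and then a second lens. Section 3, item 4, gives the number "enrolled in this entire study, across all study locations: 50". No parallel group is described.

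Section 4, item 9, sets the endpoints: "Primary endpoint is a 30% reduction in HIT-6 scores" and "Secondary endpoints are a 30% reduction in headache frequency and severity". It then defines the comparison: "The first and third months of the study serve as baseline data for subjects", and "Data collected during these two months will be compared to data collected during the second month, when study lenses are worn". The method is one sentence: "A Student's T-test should be sufficient for evaluating these data".

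The protocol does not say whether the test is paired, what one observation is, or how months 1 and 3 enter. It gives no significance level, standard deviation, correlation or power.

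**The concern.** Every child supplies both sides of the comparison, and the values are correlated within the child. Two lens-free months against one lens month is also not a simple pair, so even a reader who assumes pairing must still decide what to pair. Read literally, item 9 sets a larger body of data against a smaller one in an ordinary t-test, which is the independent-samples form. That form keeps the between-child variance in the error term, although it cancels within a child.

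At stake are the level of the test, the width of the interval for the lens effect, and most of the efficiency of a design that uses each child as his or her own control. If the choice stays open, it can be made after the data are seen, between versions that give materially different p-values.

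**Working it through.** **Inputs.** From the protocol: 50 children (section 3, item 4), and two lens-free months and one lens month per child (section 4, items 6 and 9). Assumed, because the protocol gives none of them: complete data, two-sided 5% level, equal variance σ² in each month, equal correlation r between any two months of a child, and a lens effect of 0.3 SD for the power figures. The protocol has no power figure to reproduce. Write M1, M2, M3 for a child's monthly values.

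**True variance of the contrast.** For one child, (M1 + M3)/2 − M2 has variance σ²(1−r)(¼ + ¼ + 1) = 1.5σ²(1−r). Averaged over 50 children this is 1.5σ²(1−r)/50 = 0.03σ²(1−r).

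**Version A: unpaired, 100 lens-free against 50 lens values.** The test assumes a variance of σ²(1/100 + 1/50) = 0.03σ². Its standard error is therefore too large by √[0.03/(0.03(1−r))] = 1/√(1−r). The actual type I error is 2[1 − Φ(1.96/√(1−r))].

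- At r = 0.5 the factor is 1/√0.5 = 1.41, and the error is 2[1 − Φ(2.77)] = 0.0056, about 0.6%.
- Power for 0.3 SD at r = 0.5: the assumed SE is √0.03 = 0.173 SD, so rejection needs a difference above 1.96 × 0.173 = 0.339 SD. The true SE is √0.015 = 0.122 SD. Power is Φ[(0.3 − 0.339)/0.122] ≈ 37%.

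**Version B: M1−M2 and M3−M2 stacked as 100 independent differences.** Each has variance 2σ²(1−r), so the assumed variance of their mean is 2σ²(1−r)/100 = 0.02σ²(1−r). The true variance is 0.03σ²(1−r), larger by 1.5. The actual type I error is 2[1 − Φ(1.96 × √(2/3))] = 2[1 − Φ(1.60)] = 0.110, whatever r is.

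**Version C: one contrast per child, one-sample t-test on 50 values.** The assumed and true variances agree, so the level is held. At r = 0.5 the normal approximation gives power Φ(0.3/0.122 − 1.96) ≈ 69%. The t-test with 49 degrees of freedom gives 67% by simulation.

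Simulation with 20,000 trials per setting:

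| r | A: type I / power | B: type I | C: type I / power |
|---|---|---|---|
| 0.3 | 2.0% / 39% | 10.8% | 4.7% / 53% |
| 0.5 | 0.6% / 37% | 11.2% | 5.0% / 67% |
| 0.7 | 0.06% / 34% | 10.8% | 5.1% / 87% |

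Averaging months 1 and 3 first does not help if the test then stays unpaired (50 against 50): at r = 0.5 the type I error is 0.4% and power 29%.

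**Diary days as the unit, unpaired (secondary endpoints only).** Simulation with 28 days per month, a between-child share of 30% of the variance, and 2,000 trials per setting gives a type I error of 1.7%, 18%, 28% and 43% when the child-by-month share is 0, 5%, 10% and 20%. These shares are assumptions. With none of that variance the test is conservative; with a modest amount it is clearly liberal. On the same data the test on one contrast per child gave 3.9% to 4.9%.

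**The case against.** The strongest reply is that a paired t-test is also a Student's t-test. Item 9 does not choose the two-sample form. There is one cohort, and treating months 1 and 3 as the subjects' own baseline fits a within-subject comparison. Item 9 asks only for a summary, and a statistical analysis plan that is not shown may settle form and unit. All of this stands. A reader might infer that the protocol prescribes an independent-samples test and that its p-values and intervals will therefore be wrong. The text does not support that, because one of the runs it permits is correct. Nor can one say from this document that no other analysis is planned.

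A second tempting inference is that counting diary days as independent inflates the false-positive rate of the trial's main result. It cannot: the primary endpoint is HIT-6, completed at visits. Headache frequency, too, is most naturally a count per child and month. The day-level risk is confined to the diary-based secondary endpoints, and its size rests on variances the document does not give.

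The layout of 100 against 50 is also a model. HIT-6 has four values per child, counting enrolment, and a second-lens period adds data that item 9 does not place. This qualifies the figures, but it also adds choices that the sentence leaves open.

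The reply does not remove the point. Item 9 goes beyond silence: it declares a test sufficient for a two-against-one structure that no standard t-test takes without a further rule. Assuming pairing does not rescue it, since stacking the pairs gives about 11%. Whether a test of a mean difference answers an endpoint worded as a 30% reduction is a separate question, not settled here.

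**Conclusion.** The point holds conditionally. Unless the t-test is run on one within-child contrast, its p-values and intervals will be wrong, in a direction set by the version used. With 50 complete children and equal between-month correlation, the unpaired subject-month version is too conservative: at r = 0.5 the standard error is 1.41 times too large and power is 37% against 67% for a 0.3 SD effect. The stacked-pairs version is too liberal, at about 11% for any r. The correlation and the effect size are assumptions. The 1/√(1−r) factor and the 11% follow from the two-against-one layout and the equal-correlation model. It should not be reported as a finding that the trial's results are wrong; it is an unsafe method statement that needs tightening before the data are analysed.

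**What to change.** Replace the t-test sentence in section 4, item 9, with wording such as:

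> For each endpoint, diary data are first summarised per subject and month. Each subject contributes one contrast: the mean of the month 1 and month 3 values minus the month 2 value (for HIT-6, the mean of the end-of-month-1 and end-of-month-3 scores minus the end-of-month-2 score). The contrast is tested with a paired (one-sample) t-test and reported with a 95% confidence interval.

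Add that the second-lens period is not part of this contrast, and which lens-free weeks count as month 3 for the children who go on to a second lens. A linear mixed model with month as fixed effect and subject as random effect, testing the same contrast, is an acceptable equivalent. With a random intercept only, it relies on equal correlation between months.

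The cost is a few sentences in item 9, with no extra data, visits or subjects.

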**List by name, role, and affiliation any others who will obtain consent (e.g. [name], Co-Investigator, etc.).**

2. **Describe the location(s) where consent will be obtained.**

Primary Children's Medical Center in SLC and in Riverton

3. **Describe the consent process(es), including the timing of consent. Describe whether there is a waiting period between the consent process and obtaining consent from the participant (i.e., any time between informing participants and actually obtaining consent).**

Because subjects will not undergo any intervention for one month, there will be no waiting period between the consent process and obtaining consent.

Informed consent for all potential research participants will be obtained by a member of the research team who does not have any conflicts of interest related to this research or by an appropriate third party approved by the Individual Conflict of Interest Committee.

Update for Continuing Review 2016: Authorization to obtain consent is now limited to [name] and [name].

Update for Amendment Changing PI to [name]: Authorization to obtain consent is now limited to [name].

4. **Describe what measures will be taken to minimize the possibility of coercion or undue influence.**

Study personnel obtaining consent will emphasize to potential participants that participation is strictly voluntary and that their decision to participate, or not participate, will not affect their care.

5. **Describe the provisions that are made to allow adequate time to exchange information and questions between the investigator and participant.**

Study personnel will ask potential families if they'd like more time to make a decision about participation. Study personnel will ask potential families if they'd like to discuss the research with other family members or friends before making a decision to participate.

6. **Will a legally authorized representative (LAR) be used?**

Yes  No

7. **Will a language other than English be used to obtain consent?**

Yes  No

8. **Are you requesting that documentation of informed consent be waived by the IRB (a consent process in place, but no documentation of consent, e.g. questionnaire cover letter, web-based consent, consent without signature, etc.)?**

Yes  No

**If yes, complete the following:**

- a. **Explain why the waiver of consent documentation is being requested.**

**b. Justification for the waiver is one of the following:**

There are no items to display

IRB\_00065178

Created: 5/5/2013 4:38 PM

PI: [name]

Submitted: 7/17/2013

**Title:** Thin film spectacle coatings to reduce light sensitivity and headaches in child and adolescent patients with migraine

## 5. Data Monitoring Plan

- 1. Privacy Protections:** Privacy refers to persons and to their interest in controlling access of others to themselves. Privacy can be defined in terms of having control over the extent, timing and circumstances of sharing oneself (physically, behaviorally, or intellectually) with others. **What precautions will be used to ensure subject privacy is protected?**

**Select all that apply:**

The research intervention is conducted in a private place

Discussing the study with participants individually instead of in front of a group

The collection of information about participants is limited to the amount necessary to achieve the aims of the research, so that no unneeded information is being collected

Allowing for anonymous submission of surveys and questionnaires

**Other or additional details (specify):**

- 2. Confidentiality Precautions:** Confidentiality is an extension of the concept of privacy; it refers to the subject's understanding of, and agreement to, the ways identifiable information will be stored and shared. Identifiable information can be printed information, electronic information or visual information such as photographs. **What precautions will be used to maintain the confidentiality of identifiable information?**

